Step 3. Review with YAB. Drs. [name] and [name] will facilitate the review of the mLab App user interface, content, and function with the YAB. Through our review, we will ensure that the mLab App is culturally appropriate for both YMSM and YTGW. [name] will insert changes directly into the mLab App mock-ups viewed on a screen, supplemented by note-taking by study staff and audio-recorded. This allows us to confirm meaning, make revisions as necessary, and reach consensus with the YAB. [name] will probe for further discussion on feasible ways forward and to ensure that the mLab App meets the current prevention guidelines. We will incorporate the recommended changes. As a final step, we will have members of the YAB test the final mLab App after the meeting in their own settings (e.g., Home) and return any comments or additional edits within 2 weeks. Final recommendations for the user interface will be shared with [name], who will work with his team and the graphic design team at Little Green Software (see letter of support) to make the final updates to the app.

Aim 2: Evaluate the efficacy of the mLab App in improving both HIV testing rates and linkage to care versus standard preventive care in 525 Black, Latino and other young men and transgender women (inclusive of YMSM and YTGW age 18-29 years) in a 12-month multi-site trial, with randomization at each site to three groups arm 1: intervention (mLab App) (N=210); arm 2: standard of care HIV information control arm (N=210); arm 3: OraQuick home test kits only (N=105).

Hypothesis 1. Youth randomized to the mLab App arm, as compared to youth in the standard of care HIV information control arm, will have: a) increased rates of HIV testing within the first 6 months of the trial; and b) increased rates of re-testing in months 7-12 of the trial.

Hypothesis 2. The total number of youth who test HIV positive and link to care in the mLab App arm will be greater as compared to the standard of care HIV information control arm.

Hypothesis 3. The image processing in the mLab App will: 1) have no statistically significant difference in sensitivity or specificity when compared to confirmatory testing, 2) have greater sensitivity and specificity when compared to the user-submitted self-analyses.

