Design Overview. A randomized controlled trial will be conducted with 525 young men over 12 months. Participants will be randomly assigned to the mLab App arm 1 (intervention) or a control arm 2 (standard of care HIV testing information arm) or arm 3 (OraQuick HIV home tests).¹²⁷ Participants in arm 1 will receive access to the mLab app and HIV home test kits, those in arm 2 will receive standard of care HIV information only. The primary comparison will be between arms 1 and 2. Participants in arm 3 will receive HIV home tests kits, but not access to the mLab app. Participants in all arms will receive standard preventive care at baseline. **Recruitment.** Our recruitment activities will mirror those described in Aim 1. Step 2. We will recruit youth from both Chicago and NYC as well as the entire state of Illinois and neighboring states of Wisconsin,

Michigan and Indiana in the Midwest; and all of the state of New York and neighboring states of Connecticut and New Jersey. We will recruit on Grindr and other social media using banner or pop-up ads that target YMSM and YTGW from these areas.

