Alternatives and Potential Limitations. Given that participants must be HIV negative to participate in the study, HIV testing will be included as the final screening component to verify study status prior to enrolling. This will help ensure that participants are not falsifying information on their screeners to enroll in the study. Importantly, participants are expected to continue normal healthcare activities during the course of the study and to be offered HIV testing referral information and on-site testing through existing service providers.

Arm 2- Standard of care HIV information control arm. Youth will receive standard-of-care HIV/STI testing-related risk reduction counseling, a box of condoms, PrEP assessment, and referral information for clinics that provide PrEP during your first visit. Youth randomized to arm 2, standard of care control, will be sent an email or text with links to mobile-optimized online prevention information, including PrEP and HIV testing information that is found on the CDC website.¹²⁷ They will also receive a study information card listing the Columbia University School of Nursing / Lurie Children's study teams' contact information. Once youth are randomized, they will be analyzed according to their original assignment (i.e., intent-to-treat).

Arm 3-HIV home testing arm. Youth randomized to arm 3 will be provided with the 2 OraQuick tests (including the package insert), and a box of condoms to take home at baseline. They will receive 2 more OraQuick tests at the 6 month visit. Participants may come in person to receive their tests or their tests may be mailed to them at their verified address if they are unable to complete an in-person 6 month visit. OraQuick tests will be sent via tracked shipping through USPS, FedEx, UPS. At their baseline appointment, youth will also be sent an email or text with links to mobile-optimized online prevention information, including PrEP and HIV testing information that is found on the CDC website. They will also receive a study information card listing the Columbia University School of Nursing / Lurie Children's study teams' contact information

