Arm 1-Intervention Arm (mLab App + HIV home test). Youth randomized to the intervention arm will be provided with the mLab App, 2 OraQuick tests (including the package insert), and a box of condoms to take home at baseline. They will receive 2 more OraQuick tests at their 6 month visit. Participants may come in person to receive their tests or their tests may be mailed to them at their verified address if they are unable to complete the in-person visit. The OraQuick tests will be sent via tracked shipping through USPS, FedEx, and UPS. At their baseline appointment, youth will also be sent an email or text with links to mobile-optimized online prevention information, including PrEP and HIV testing information that is found on the CDC website. They will also receive a study information card listing the Columbia University School of Nursing / Lurie Children's study teams' contact information. The goal of the mLab App is not for partner testing. We will advise participants upon study enrollment and consent (see Protection of Human Subjects) that the technology is NOT to be used for this purpose in this study. Given this limitation, we will suggest that participants who have partners who are interested in testing should contact the study team in each respective city for more information on HIV testing. We will also reinforce with participants that the mLab App is considered a screening device and they should seek confirmatory testing (for both negative and positive test results). The mLab App is mobile app on your phone that is accessible using a login name and password. The app will provide HIV prevention information, push notification reminders for testing, step-by-step instructions for using the OraQuick HIV tests, an image upload function to send an image of your OraQuick HIV test to the study team.

Participants will:

- a) be asked to manually enter the Oraquick test results; and
- b) take a picture of the test results for the app to analyze the results; and

- c) receive the app's interpretation of the Oraquick test results.

By using the app, we are asking participants to help test the app's ability to interpret the results of the OraQuick tests. If you test HIV positive by the OraQuick HIV test and/or the mLab app will provide information on how to set up follow-up confirmatory testing within the following 24 hours. All information that you provide within the app will be stored on a secured server at Vanderbilt University

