All multivariate analyses will be preceded by standard descriptive bivariate analyses to describe the key variables and relationships among them. These analyses will include means, frequency tables, histograms, and examination of distributions. Frequencies and rates of HIV tests, as well as corresponding confidence intervals, will be calculated for each arm. All statistical tests will be two-sided tests with the level of significance at 0.05. Hypotheses testing will be based on logistics models to compare (1) HIV testing during the first 6 months; and (2) HIV re-testing at 7-12 months between the mLab App arm and the control (*Hypothesis 1*). We will conduct stratified analyses to examine the differences in testing uptake in subgroups (i.e., racial/ethnic, age, YMSM vs. YTGW, and risk level). Effect sizes will also be compared between arms 1 and 3 to describe differences in testing and linkage behavior attributable to the mLab app with home test distribution versus home test distribution only. Linkage to care will be measured by the percent of study participants who tested positive and

attended a first HIV care appointment at NYP/Columbia or Lurie or who provide documentation of care at another clinic and the time to link to care after positive result. Follow-up surveys for HIV positive participants will also include questions regarding positive diagnosis, such as disclosure and seeking care. For participants who test HIV positive, we will compare the rates of linkage to care between the mLab App arm and the control arm using Fisher's exact test (*Hypothesis 2*). However, because the number of positive (HIV) tests is expected to be approximately 25-40, this part of the study will not have power to detect a significant statistical difference between groups.

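### Aim 2 calls the arm 1 versus arm 2 result the app's efficacy, but that contrast measures app plus kits, and no interval is planned for the arm 1 versus arm 3 difference that could isolate the app

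*Combined protocol and SAP*

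**What the plan says.** Aim 2, stated under Study Aims and again under Study Procedures, is: "Evaluate the efficacy of the mLab App in improving both HIV testing rates and linkage to care versus standard preventive care". The Design Overview adds "The primary comparison will be between arms 1 and 2" and says what each arm gets. Arm 1 has the app and home test kits, while "those in arm 2 will receive standard of care HIV information only". Arm 3 has kits without the app. The sections on arms 1 and 3 give both the same kit supply: two at baseline and two more at 6 months.

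Under Data Analysis, the logistic models for Hypothesis 1 and Fisher's exact test for Hypothesis 2 compare arm 1 with the control arm. For arm 3 the plan is: "Effect sizes will also be compared between arms 1 and 3 to describe differences in testing and linkage behavior", namely those "attributable to the mLab app with home test distribution versus home test distribution only". On intervals it says: "Frequencies and rates of HIV tests, as well as corresponding confidence intervals, will be calculated for each arm". It names no effect measure, interval or expected precision for the arm 1 versus arm 3 difference.

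**The concern.** Arms 1 and 2 differ in two things at once: the app and the free kits. The primary outcome is self-reported HIV testing in the past 6 months, and kits alone could raise that. The plan's own assumptions point the same way. The sample size section takes its effect size from a trial of self-testing and cites no app component for the move from 40% to 60%.

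If Aim 2 is followed as worded, a positive primary result could be reported as efficacy of the app when some or all of it came from handing out kits. The contrast that can separate the two is arm 1 against arm 3. As planned, its output would not show a reader how little or how much the trial can say about the app.

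**Working it through.** **What each contrast isolates.**
- Arm 1 versus arm 2: app plus kits against neither.
- Arm 1 versus arm 3: same kit supply, with and without the app.

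**Inputs from the documents.** Randomised: 210, 210 and 105. Attrition: 20% at 6 and 12 months, which leaves 168, 168 and 84. Testing rates: 40% control and 60% intervention. Two-sided alpha: 0.05. No kits-only rate is given, so k = 45% to 60% is an assumption.

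**The plan's own figure.** The plan claims at least 80% power for the two Hypothesis 1 tests. For one test with 168 per arm, 60% versus 40%:
- Standard error under no difference = √(2 × 0.5 × 0.5 / 168) = 0.0546.
- Standard error under the alternative = √((0.24 + 0.24) / 168) = 0.0535.
- z = (0.20 − 1.96 × 0.0546) / 0.0535 ≈ 1.74, so power is about 96%.

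If each test is run at 0.025, power is 92.7% per test, and at least 2 × 0.927 − 1 ≈ 85% for both. This assumes that 40% and 60% also apply in months 7 to 12, for which no separate rates are given. The stated figure holds, for the package.

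**Precision of arm 1 minus arm 3.** The 95% half-width at no difference is 1.96 × √(k(1 − k)(1/n₁ + 1/n₃)). For k = 0.50 with 168 versus 84: 1.96 × √(0.25 × 0.01786) = 0.131. The last column fixes arm 1 at the planned 60% and uses 1.96 × √(0.24/168 + k(1 − k)/84).

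| Assumed kits-only rate | Half-width, 168 vs 84 | Half-width, 210 vs 105 | Expected interval, arm 1 at 60%, 168 vs 84 |
|---|---|---|---|
| 45% | 13.0 points | 11.7 points | +2 to +28 |
| 50% | 13.1 points | 11.7 points | −3 to +23 |
| 55% | 13.0 points | 11.7 points | −8 to +18 |
| 60% | 12.8 points | 11.5 points | −13 to +13 |

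These are unadjusted figures for completers, or for everyone observed. The planned analysis imputes missing outcomes, so they are approximate.

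**Why per-arm intervals do not replace this.** At 60% versus 45% the two arms' intervals are 52.6% to 67.4% and 34.4% to 55.6%. They overlap, yet the interval for the difference excludes zero. Among the four rates shown this happens only at 45%. The more general point is that a reader cannot see the width of the difference without its interval.

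**The case against.** The strongest reply is that nobody reading the full protocol would be misled. Aim 2 names its comparator, its restatement under Study Procedures lists arm 3 as kits only, the Design Overview says what each arm receives, and the section on arm 1 is headed as app plus home test. The hypotheses compare named arms. The app's testing function needs a kit, so its name can serve as shorthand for the whole intervention. The Data Analysis section already picks the right contrast for attribution. A risk difference is an effect size, and silence about an interval does not mean that it will be left out.

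Much of this stands, and it limits the point to wording and one unspecified estimate. It does not remove it. The protocol treats app and kits as separable, since arm 3 differs from arm 1 in the app while getting the same kits. A contrast meant to describe what the app adds also needs a stated measure and interval, because a descriptive result from a small arm is easily over-read in either direction.

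A reader might go further and infer that the primary comparison is invalid or underpowered, that the role of the kits is concealed, or that the trial has no means of isolating the app. The documents support none of these. Nor do they imply that arm 3 must be enlarged: the contrast is presented as descriptive, and no test of it is planned or needed.

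**Conclusion.** The point holds as a matter of attribution and reporting. Arm 1 versus arm 2 is a sound test of app plus kits against information only, and Aim 2 labels it more broadly than it can bear. The app-specific contrast is present but unspecified. Its likely precision is about ±13 points with 168 versus 84 completers and about ±11.5 if all 210 versus 105 are observed. Both depend on an assumed kits-only rate of 45% to 60% and on unadjusted calculation.

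One qualification applies to arm 1 versus arm 3. The image-processing and risk-protection sections give arm 1 staff review of uploaded images, and staff contact when the app's result is wrong or differs from the participant's own reading. For re-testing and linkage, the contrast is therefore the app with that support. A reader might extend this to all testing outcomes, but review follows an uploaded test and so cannot produce a first test.

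**What to change.** Keep arm 1 versus arm 2 as the primary comparison, and make these changes:

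- In both statements of Aim 2, and in the conclusion drawn from it, use *mLab App plus home test kits versus information only*.
- Under Data Analysis, replace the effect-size comparison for testing with the arm 1 minus arm 3 risk difference and its 95% confidence interval, for the first 6 months and for months 7 to 12, as a secondary estimate. Use the same multiple imputation and intention-to-treat rules as the primary analysis, and account for the site strata used in randomisation.
- Leave the arm 1 versus arm 3 linkage comparison descriptive.
- State that app-specific claims rest on this estimate, give its approximate precision with the assumed kits-only rate, and note that for re-testing and linkage arm 1 includes staff image review and contact.

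This costs some rewording and one estimate from data already being collected. Arms, sample size, randomisation and the primary test are unchanged. The downside is a narrower headline claim and an openly imprecise estimate for the app itself.

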Eligibility criteria. In addition to the eligibility criteria listed in Aim 1 – End-User Usability Testing, we will also include the following eligibility criteria: 1) understand the limitations of the OraQuick test and the mLab App (e.g., a confirmatory test is needed – see Protection of Human Subjects); 2) not having been tested for HIV in the past 6 months (e.g., therefore being somewhat outside of the current CDC testing recommendations for high-risk populations – see below). 3) not currently taking PrEP and 4) receive a non-reactive result on the rapid HIV test at the baseline visit

Alternatives and Potential Limitations. *We carefully considered the frequency of testing for our study participants and have agreed that participants should test at least every 3-6 months based on the following 2 considerations:* 1) Current CDC guidelines recommend annual testing and more frequent (every 3-6 months) for sexually active MSM at high-risk for HIV infection based on individual risk factors.^{129, 130} 2) Since all of our participants meet the criteria for use of PrEP¹⁰⁷ and based on our clinical experience for interpretation of these guidelines, we have specified that our study participants should test a minimum of every 3-6 months.^{27,28} As part of the intervention, participants in arm 1 will be reminded to use the OraQuick tests at 3 month, 6 month, 9 month, and 12 month time points through the mLab app.

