mLab Image-Processing Evaluation Methods. During use of the mLab App, participants will submit images of their Oraquick self-test to the app for analysis by an automated image-processing algorithm. Prior to submitting this image for analysis, participants will be asked to interpret the results of the test using the instructions that are provided standard with the OraQuick test. This self-reported result will be recorded and uploaded with the user-submitted image of their rapid test. Study team members with expertise in rapid test use and analysis will evaluate the uploaded images of each rapid test, and provide an additional assessment. The user-submitted result and the study team assessment will not be used by mLab in its automated image-processing. All users that submit tests that are identified as positive, either by the automated image-processing in mLab, the study team personnel's inspection of the image of the rapid test, or by the study participant themselves, will be referred for confirmatory testing.

(*Hypothesis 3*).**mLab Image-Processing Data Analysis Plan.** Including the confirmatory test, which will be treated as the gold standard to determine whether a test result is truly false or positive, there will be results from four analysis methods collected on the same set of tests (1. User-submitted results, 2. Study team interpretation of uploaded images, 3. Automated mLab App results, 4. Confirmatory testing). The sensitivity and specificity for each of these methods will be compared using McNemar's test. This will result in the following statistical comparisons for both sensitivity and specificity: 1) user-submitted analysis to study team analysis, 2) user-submitted analysis to mLab analysis, 3) study team analysis of uploaded images, 4) user-submitted analysis to confirmatory testing, 5) study team analysis to confirmatory testing, 6) mLab analysis to confirmatory testing.

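### Hypothesis 3 tests app sensitivity on too few positive strips: a null result for part 2 would say little, and part 1 could be met through scarcity alone

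*Combined protocol and SAP*

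**What the plan says.** Hypothesis 3 appears in Study Aims and again under Aim 2. Part 1 expects no significant difference in sensitivity or specificity between the app and confirmatory testing. Part 2 expects the app to "have greater sensitivity and specificity when compared to the user-submitted self-analyses". The mLab Image-Processing Data Analysis Plan treats the confirmatory test as the gold standard and states: "The sensitivity and specificity for each of these methods will be compared using McNemar's test". It does not say which form of the test. The Data Analysis section adds: "All statistical tests will be two-sided tests with the level of significance at 0.05".

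Three other places limit the number of positive strips:

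- The Aim 2 eligibility criteria require that a participant "receive a non-reactive result on the rapid HIV test at the baseline visit".
- The Design Overview gives arm 2 information only, and says of arm 3: "Participants in arm 3 will receive HIV home tests kits, but not access to the mLab app". Only arm 1 uploads strips.
- The Data Analysis section expects roughly 25-40 positive tests. It concedes that "this part of the study will not have power to detect a significant statistical difference between groups", but this closes the account of the linkage comparison in Hypothesis 2.

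The sample size section rests on Hypothesis 1. Hypothesis 3 has no expected count, power, precision target or caveat.

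**The concern.** Sensitivity is estimated only on strips from infected people. Everyone enters with a non-reactive result, so these strips can come only from arm 1 participants whose infection becomes detectable after entry and who then self-test and upload. McNemar's test narrows the information further, because it uses only the strips on which two readings disagree.

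Scarcity acts in opposite directions on the two parts. In part 2, a superiority claim, it makes success unlikely, and failure would say little about whether the app reads positives better than users do. In part 1, where a non-significant result counts as support, it makes success easy. Part 1 is the more serious problem: the protocol's risk sections call the app's accuracy unproven and its results investigational, yet the planned analysis could end in an apparent finding of sensitivity equal to confirmatory testing.

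**Working it through.** **The protocol's own figure.** The 25-40 positives cannot be reproduced, because no HIV incidence is given. Over 525 participants they imply 25/525 = 4.8% to 40/525 = 7.6% in a year.

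**Arm 1's share (assumed).**
- By allocation: 210/525 = 40%, so 10-16 positives.
- If the figure covers only arms 1 and 2 (equal in size) and detection follows the planning testing rates of 60% and 40%: 60/(60+40) = 60%, so 15-24.

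**Disagreements needed at two-sided 0.05, all in one direction.**
- Exact: p = 2 × 0.5^k. k = 5 gives 0.0625 and k = 6 gives 0.031, so at least 6.
- Continuity-corrected: (k−1)²/k. k = 5 gives 3.2 (p = 0.074) and k = 6 gives 4.17 (p = 0.041), so again 6.
- Uncorrected chi-square: equal to k. k = 4 gives p = 0.046, so at least 4.

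**Part 2.** With a perfect app, every disagreement on a positive strip is a user misread. The chance of significance is P(Binomial(n, m) ≥ 6) for the exact test or ≥ 4 for the uncorrected test, where m is the user misread rate. The documents give no value for m, so a range is shown. Cells are exact / uncorrected.

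| Positives n | m = 10% | m = 20% | m = 30% |
|---|---|---|---|
| 10 | <0.1% / 1.3% | 0.6% / 12% | 4.7% / 35% |
| 15 | 0.2% / 5.6% | 6.1% / 35% | 28% / 70% |
| 16 | 0.3% / 6.8% | 8.2% / 40% | 34% / 75% |
| 24 | 2.8% / 21% | 34% / 74% | 77% / 96% |

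One of the 24 entries exceeds 80%. Solving the same formula for 80% power gives these misread rates, to the next whole percent:
- exact: 68% (n = 10), 45% (n = 16), 31% (n = 24);
- uncorrected: 49%, 32%, 22%.

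An imperfect app lowers the chance. With app sensitivity 95%, user sensitivity 80% and independent errors, it is 0.4% (n = 10) to 4.2% (n = 16) exact, or 7.8% to 21% uncorrected.

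**Part 1.** The confirmatory test is the reference, so on a truly positive strip every disagreement is an app miss. The exact test stays non-significant with up to 5 misses. Observed sensitivities of 5/10 = 50%, 11/16 = 69% and 19/24 = 79% would therefore all count as no significant difference. For an app that truly misses 20%, the chance of meeting part 1 is one minus the m = 20% entry above:
- exact: 99% (n = 10), 92% (n = 16), 66% (n = 24);
- uncorrected: 88%, 60%, 26%.

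**Precision.** For n of n read correctly, the exact 95% lower bound is 0.025^(1/n): 69% (n = 10), 79% (n = 16), 86% (n = 24). Even a flawless record would leave sensitivity loosely bounded.

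**The case against.** A reader might infer that the eligibility rule contradicts the hypothesis. It does not. A non-reactive baseline does not prevent infection during follow-up, and the protocol expects its 25-40 positives under that same rule.

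A reader might also infer that part 2 must fail however well the app performs. That is too strong. The form of McNemar's test is not specified, and the uncorrected form needs only 4 disagreements. With 24 positives it reaches 80% power once users misread 22%. If all 25-40 positives fell in arm 1, a 20% misread rate would give 38%-84% with the exact test. The arm 1 share and the misread rate are this review's assumptions. Incidence rates low enough to leave arm 1 with only a handful of positives can be imagined, but no document supplies one, and the conclusion does not need it.

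The sponsor can fairly add that power is claimed for Hypothesis 1 only, that app performance is described as a secondary goal, and that the manual read is the result of record. All of that stands. It does not answer the point, because sensitivity remains a tested claim. The caveat sits with Hypothesis 2, which draws positives from arms 1 and 2, whereas Hypothesis 3 can draw on arm 1 alone.

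**Conclusion.** The concern holds as one of low information. At 10-24 positives, with a perfect app and 20% user misreads, the chance of a significant part 2 result is about 0.6%-34% (exact) or 12%-74% (uncorrected). At 10% misreads it is at most 21%. It passes 80% only if users misread many more positives or nearly every assumption is favourable. A null result in part 2 would therefore be uninformative, and part 1 could be met because positives are few.

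These figures treat strips as independent; repeat positive strips from one person would carry less information. Infections that all three readers miss are not routinely referred, so they would not enter the sensitivity denominator, and observed sensitivities may run high. Hypothesis 1 is unaffected.

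**What to change.** In both statements of Hypothesis 3 (Study Aims and Aim 2) and in the mLab Image-Processing Data Analysis Plan:

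1. Remove sensitivity from the tested claims in part 1 and in part 2. Changing part 2 alone would leave part 1 claiming no significant sensitivity difference with no test behind it.
2. Report instead the number of confirmed-positive strips and the number read correctly by app, user and study team, each with an exact 95% confidence interval.
3. Extend the no-power caveat to Hypothesis 3, and state that no conclusion of equal or better sensitivity will be drawn from a non-significant result.
4. Keep the paired app-versus-user comparison for specificity. Arm 1 may supply up to 210 × 4 = 840 strips, nearly all negative, but the plan should not presume a reference result for each. The Image-Processing Evaluation Methods refer strips that some reader calls positive, and the intervention-arm risk procedures refer participants who test negative only on request, although the arm 1 description advises confirmation of both results. App-user disagreements would be referred, but most strips that all readers call negative may have no reference result. The plan should say how those are counted.

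The cost is wording, with no new data or procedures. The sponsor gives up a formal sensitivity claim that the trial is unlikely to support.
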